#### Criteria of success:

- We will document best response in all patients. Patients shall be followed for at least six months on treatment (providing their tumors do not progress earlier) in order to document best response: The trial will be considered as meeting its primary endpoint if a 6-month response rate (% of patients achieving RECIST 1.1 complete or partial response within 6 months of treatment start) of 50% is achieved for patients who are fully matched according to the SIMS retrospective analysis and is superior to the partially matched arms. With a type I error of 10% and a power of 94%, 20 patients fully matched will be enough to demonstrate the usefulness of the approach assuming a null response rate of 20% based on the one-sided Fisher's exact test. This would require a cohort of 200 patients treated. Nevertheless, we intend to treat an initial cohort of 100 patients as an exploratory observational study. Pending clinical activity, the study could be extended to an additional 100 patients treated in order to attain sufficient statistical power to support the validity of the approach.
- SIMS will show clinical utility:
  - If the proportion of patients fully matched to the combination versus partially matched estimated using SIMS (20/80) is similar to the observed proportion in the SPRING cohort (maximum coefficient variability allowed 20%),
  - If fully matched patients show significantly better clinical outcomes than the partially matched ones and the fully or partially matched ones show significantly better clinical outcomes than the non-matched ones.

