**Recurrent Grade 3 ADRs and Grade 3 infusion-related reaction require permanent discontinuation.**

**Any Grade 2 ADR should be managed as follows:**

- If a Grade 2 ADR resolves to Grade  $\leq$  1 by the last day of the current cycle, treatment may continue.
- If a Grade 2 ADR does not resolve to Grade  $\leq$  1 by the last day of the current cycle, infusions should not be given on the following cycle. If at the end of the following cycle the event has not resolved to Grade 1, it should be treated as a Grade 3 or 4 (except for hormone insufficiencies, that can be managed by replacement therapy; for these hormone insufficiencies, up to 2 subsequent doses may be omitted).
- Upon the second occurrence of the same Grade 2 ADR (except for hormone insufficiencies that can be managed by replacement therapy) in the same subject, treatment with avelumab has to be permanently discontinued.

Important note (6):	Specific protocol dose modification for toxicity management related to palbociclib: 

- In case of recurrent grade 3 hematologic toxicities, palbociclib may be reduced to 75 mg po daily one week off and one week on.

- In case of other severe (<math>\geq</math> grade 3) toxicity related to palbociclib, consider holding palbociclib until toxicity is grade 1 or less, then resume at the alternate schedule of 2 weeks OFF / 2 weeks ON.

----------------------------	---

- **DLT will be defined as:**

Any of the following events that are considered to be clinically significant and meaningful as per evaluation of the attending physicians and confirmed by CMC and at least possibly related to drug. DLTs for the purposes of dose-escalation will be evaluated during the 28-day period following the first dose of study treatment. Each treatment cycle is four weeks. Toxicities will be graded and documented according the NCI CTCAE (v4.03).

- **Non-hematological dose-limiting toxicity is defined as:**

- Persistent Grade 3 or 4 hypertension despite treatment with anti-hypertensive drugs.
- Grade 3 or 4 Gastrointestinal bleeding.
- Grade 3 or 4 Gastrointestinal perforation or fistula.
- Development of Reversible Posterior Leukoencephalopathy Syndrome.
- Persistent Grade 3 or 4 proteinuria.
- Grade 3 or 4 arterial or venous thromboembolic events.

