The proposed study is a proof of concept protocol to evaluate the outcome of patients who receive triple therapy and to evaluate through a retrospective analysis, the clinical utility of the SIMS algorithm and integrated genomic/transcriptomic analysis. For the selected triple combination therapy, we will incorporate a seamless Phase 1/2 design with a limited Phase 1 run-in to determine the recommended Phase 2 dose for the regimen. Patients enrolled in the phase 1 study who receive the RP2D will also be included in the phase 2 efficacy assessment. In the first part of the phase 2 study, up to 100 patients will receive the triple combination therapy and all will have dual biopsies in order to obtain the full set of genomic and transcriptomics data resulting from the investigation of matched tumor and normal biopsies. The population for analysis of response (evaluable patients) will be those that received at least one cycle of treatment. The SIMS algorithm will not be used prospectively to assign patients to treatment. However, it is expected that the SIMS score for each patient will be available within 3 months after the treatment start date. SIMS algorithm will be used retrospectively for defining patient subgroups and correlation correlating with treatment outcome. Patients will be stratified into the fully matched group (Arm A) with all three interventional points activated, or partially matched group, with one or two interventional points activated (Arms B1-B3, C1-C3) or the non-matched group (Arm C4) (see study schema). In addition, after completion of the clinical trial, a correlation study will be performed between patients' clinical outcomes and the predicted match determined by SIMS and all potential prognostic and predictive variables. The primary endpoint for this study is defined as the 6-month objective response rate (by RECIST 1.1 criteria as percent of patients achieve complete response, or partial response). We choose the 6-month response rate for an early efficacy read of the triple therapy. Other efficacy endpoints may include best overall response rate, progression-free survival (PFS), overall survival (OS). The expected result is a better clinical outcome in the fully matched patients arm (arm A) as compared to the partially matched or the non-matched patients' arms.

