## 7.2. PHASE 2 EFFICACY EVALUATION

The Phase 2 study will be conducted in two parts. In the first part of the Phase 2 study, we expect to enroll approximately 120 patients in order to obtain 100 patients eligible for the study treatment. Futility early stopping rule will be implemented to ensure that the treatment has met the minimum efficacy requirements. If not meeting the minimum efficacy requirement, the trial will be stopped early. If the trial is not stopped early after the first 100 patients, the study could be extended, (with an amendment) to the second part of the Phase 2 study in order to reach a total of 200 patients treated.

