### 7.2.1. Statistical analysis of the primary efficacy end point

The primary efficacy evaluation for measuring a clinical meaningful improvement is defined as demonstrating an improvement of the primary efficacy endpoint of 6-month objective response rate from 20% (under the null hypothesis) to 50% (under the alternative hypothesis) in the fully matched arm. With 5% one-sided type I error, we need to treat 20 patients to demonstrate the usefulness of the tri-therapy approach to achieve and 86% power based on the exact binomial test. With an expected 10% of patients who will be fully matched, we need to enroll 200 patients in the study. All inevaluable patients will be replaced. **To ensure that patients will not receive ineffective treatments after sufficient evidence, two efficacy futility early stopping rules** will be implemented.

- The first futility early stopping rule will be applied after treating 14 patients with the tri-therapy at the RP2D level. If none of the 14 patients has 6-month response (CR or PR), the patient enrollment will be halted and the trial can be stopped for futility. This futility early stopping rule coincides with the first stage of the Gehan's design targeting 20% response rate with 95% confidence (26).
- The second futility early stopping rule will be evaluated every 10 patients after 20 patients are treated at the RP2D by applying the predictive probability (27). The trial can be stopped early if we see the following 6-month responses or less: 2 in 20, 3 in 30, 5 in 40, 6 in 50, 7 in 60, 9 in 70, 11 in 80, or 12 in 90 patients. The design has 5% type I error rate and 95% power with a null response rate of 10% and a target response rate of 30% at 6 months in the whole group. The probability of early stopping is 0.95, 0.31, and 0.04 if the response rate in the whole group is 10%, 20%, and 30%, respectively.

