 Free T4 and TSH must be performed at baseline and at least every 8 weeks during treatment and at end of treatment or 30 days post-treatment safety follow-up (if not performed in the previous 8 weeks).

 Hematology and Chemistry tests and urinalysis (see section 5.4) should be performed every week +/- 3 days during the first cycle and then every 2 weeks +/- 3 days prior the avelumab infusion.

 Baseline scan within 28 days of the start of therapy and follow-up scans about every 8 weeks (+/- 7 days): end of C2, C4, C6, etc.

 Avelumab is administered at the study site at D1 (-1/+3 days) and D15 (-1/+3 days) of each cycle. Premedication in order to mitigate infusion-related reactions, with an antihistamine and with paracetamol (acetaminophen) should be given 30 to 60 minutes prior to avelumab infusion for at least the 4 first doses. Following avelumab infusions, patients must be observed for 30 minutes post-infusion for potential infusion-related reactions.

 Axitinib is taken every day orally at home. Treatment diary should be provided to the patient to record treatment intake and side effects.

 Palbociclib is taken orally from day 8 to day 28 every cycle at home. Treatment diary should be provided to the patient to record treatment intake and side effects.

 Blood specimens will be collected for each patient enrolled at base line, before starting the treatment, one week after onset of the treatment and about every 8 weeks thereafter.

 PK Blood specimens will be collected for each patient at day 15 of each cycle (-1/+3 days according to the 2nd avelumab injection) at the following time +/- 5 minutes: before intake of axitinib and palbociclib, after 0h45, 1h15 and 2h of axitinib and palbociclib intake, 4h after axitinib and palbociclib intake and before avelumab IV, at the end of avelumab infusion, after 1h, 2h, 3h and 5h of avelumab infusion.

 The extended safety follow-up beyond 30 days after last study drug administration may be performed either via a site visit or via a telephone call with subsequent site visit requested in case any concerns noted during the telephone call.

 1 cycle = 28 days

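### The response analysis set, read plainly, drops and replaces treated patients who fail in cycle 1, which biases the primary 6-month response rate upward by a factor of 1/(1 − d), where d is the share lost

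*Combined protocol and SAP*

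**What the plan says.** Section 7 names the 6-month objective response rate as the primary endpoint and sets its analysis population: "The population for analysis of response (evaluable patients) will be those that received at least one cycle of treatment". Cycle length is given twice: "Each treatment cycle is four weeks" in the DLT definition of Section 3.3.1, and "1 cycle = 28 days" in footnote 12 of the Appendix 5 flowchart. Section 7.2.1 adds: "All inevaluable patients will be replaced".

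Other parts of the plan use a different denominator or leave it open:

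- Section 3.1 (criteria of success) states the endpoint as the percentage "of patients achieving RECIST 1.1 complete or partial response within 6 months of treatment start", with no evaluability condition.
- Section 7.2.1 expresses the sample size as 20 patients to be treated, and its futility rules also count treated patients: "The first futility early stopping rule will be applied after treating 14 patients with the tri-therapy at the RP2D level".
- Section 5.8 adds conditions on baseline and follow-up scans to the definition of an evaluable patient. They can be read as a scan schedule or as grounds for exclusion.
- Section 7.6 plans intent-to-treat and per-treatment analyses at the end. It defines neither and does not say which one decides.

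**The concern.** Patients who leave during the first 28 days are mostly treatment failures. If they are removed from the denominator and replaced by patients who got further, the numerator hardly changes and the rate rises.

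The protocol foresees early discontinuation: Section 3.3.1 lists failure to complete half of the planned treatment because of adverse events among its dose-limiting toxicities, and some grade 4 toxicities stop all three drugs permanently.

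What is at stake is the headline efficacy result, including the rate reported from the first 100 patients, on which any extension would depend. The plan also gives one endpoint more than one denominator, so two analysts could report different primary results and both be following the document.

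**Working it through.** **Inputs.** Null 20%, alternative 50%, one-sided 5% error, 20 treated patients in the fully matched arm and 86% power come from Section 7.2.1. The expected whole-group rate of 30% and the Arm A rate of 50% come from Section 7. The first scheduled on-treatment scan, at the end of cycle 2, comes from Appendix 5, footnote 5. The share d of treated patients lost in cycle 1 is **not documented**, so every value of d below is an assumption.

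**1. The plan's own figure.** Take success as at least 8 responders in 20.
- P(X ≥ 8 | 20, 0.20) = 0.032.
- P(X ≥ 8 | 20, 0.50) = 0.868, which agrees with the stated 86%.
- A rule of at least 7 in 20 has error 0.087 and so fails the 5% level.

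The ≥ 8/20 rule is therefore the one Section 7.2.1 implies. Section 3.1 gives a 10% error and 94% power for the same 20 patients; the test results below refer to the Section 7.2.1 rule.

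**2. Size of the bias.** If a share d of treated patients is dropped and none of them has a recorded response, then

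evaluable-only rate = all-treated rate / (1 − d), so all-treated rate = reported rate × (1 − d).

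| Assumed d | Reported 30% means | Reported 50% means |
|---|---|---|
| 5% | 0.30 × 0.95 = 28.5% | 0.50 × 0.95 = 47.5% |
| 10% | 0.30 × 0.90 = 27.0% | 0.50 × 0.90 = 45.0% |

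**3. Effect on the 20-patient Arm A test.** This test arises only after an extension. If the 20% null is a rate among all treated patients, the null rate among evaluable patients is 0.20/(1 − d), and the actual error is P(X ≥ 8 | 20, 0.20/(1 − d)).

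| Assumed d | Null rate among evaluable | Actual error, ≥ 8/20 |
|---|---|---|
| 0 | 20.0% | 3.2% |
| 5% | 21.1% | 4.2% |
| 10% | 22.2% | 5.7% |
| 15% | 23.5% | 7.6% |
| 20% | 25.0% | 10.2% |

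The error reaches 5% at d ≈ 7.9%. If the 20% null is already an evaluable-patient rate, the error stays at 3.2% whatever d is. Under Section 3.1's literal requirement of a 50% rate (at least 10 of 20), P(X ≥ 10 | 20, 0.20/(1 − d)) is 0.3% at d = 0 and 1.4% at d = 20%, well below 5%.

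**The case against.** **The wording is open.** Receiving at least one cycle could mean only starting cycle 1. Early failures would then stay in and the bias would largely disappear. This stands as a caveat. Completing the cycle is nevertheless the plainer reading, and a primary denominator with two readings needs a definition in any case.

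**An intent-to-treat analysis is planned, and the first cohort is exploratory.** Section 7.6 would show the lower rate and says that findings need later validation. Section 3.1 says of the first 100 patients: "Nevertheless, we intend to treat an initial cohort of 100 patients as an exploratory observational study". This softens the point without removing it. Section 7 expressly assigns the response analysis to the evaluable set, the intent-to-treat analysis is undefined, and no sentence settles a disagreement between the two.

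**The loss may be small.** Entry requires ECOG 0–1 and a life expectancy of at least 12 weeks. With no scheduled scan in cycle 1, scan-detected progression there would be off schedule. A dose-limiting toxicity need not end treatment, since drugs may be held, restarted or stopped singly. A reader might take the 33% DLT ceiling as a guide to first-cycle loss, but the documents do not support that. All of this stands, and it is why the size is given only conditionally.

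**Counting every undocumented response as a failure can bias downward,** because some withdrawals have nothing to do with efficacy. This is fair, and it is a reason to keep the evaluable set as a sensitivity analysis.

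**Conclusion.** The point holds on the plain reading: the stated population and replacement rule together bias the primary 6-month response rate upward by 1/(1 − d). At an assumed 5% to 10% loss the overstatement is 1.5 to 3 points on a reported 30% and 2.5 to 5 points on a reported 50%. This rests on two assumptions: that receiving a cycle means completing it, and that patients lost in cycle 1 have no recorded response. The scan schedule makes the second nearly certain.

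Three stronger inferences are tempting but not supported:

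- **That the trial's type I error is inflated.** The 20-patient test exists only if "the study could be extended, (with an amendment) to the second part of the Phase 2 study". Even then the ≥ 8/20 rule exceeds 5% only if the 20% null is an all-treated rate and loss is above about 7.9%. The documents give neither a source for the 20% nor a loss rate.
- **That the futility rules are weakened.** As worded they count treated patients and are not affected.
- **That the comparison between SIMS groups is biased.** Nothing in the documents indicates that early loss differs between groups, and no such bias is claimed.

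This should be fixed. Confidence is medium, because the key term is undefined and the loss rate is unknown.

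**What to change.** - Make the primary response set all patients who started treatment at the RP2D; for the Arm A test, those of them with a SIMS result.
- Count patients without a documented response as non-responders, and do not replace treated patients because of early failure.
- Keep the evaluable set as a sensitivity analysis. Define what receiving one cycle means, and say whether the scan conditions in Section 5.8 are a schedule or an exclusion.
- Align Sections 5.8, 7, 7.2.1 and 7.6 with the endpoint as stated in Section 3.1, and add one sentence naming the analysis that decides.

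**Cost.** The change is to wording and needs no new data. The reported rate will be slightly lower. If the assumed 50% was an evaluable-patient rate, power at n = 20 should be restated as P(X ≥ 8 | 20, 0.50 × (1 − d)): 87% becomes about 81% at 5% loss and 75% at 10%. No added enrolment is needed provided that lower power is accepted.

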## 7.1. SEAMLESS PHASE 1/2 TRIALS FOR THE TRIPLE COMBINATION THERAPY

For the triple combination therapy we will conduct a seamless Phase 1/2 trial to establish the safety of the regimen and to identify the recommended Phase II dose. Efficacy and safety will be assessed throughout both Phase 1 and 2. The starting dose for phase 2 will depend on the drugs administered. The target toxicity level is no more than one-third (33%) of patients experiencing dose DLT defined as Grade 3 non-hematological or Grade 4 hematological toxicities under the NCI CTCAE version 4.03.

## 7.2. PHASE 2 EFFICACY EVALUATION

The Phase 2 study will be conducted in two parts. In the first part of the Phase 2 study, we expect to enroll approximately 120 patients in order to obtain 100 patients eligible for the study treatment. Futility early stopping rule will be implemented to ensure that the treatment has met the minimum efficacy requirements. If not meeting the minimum efficacy requirement, the trial will be stopped early. If the trial is not stopped early after the first 100 patients, the study could be extended, (with an amendment) to the second part of the Phase 2 study in order to reach a total of 200 patients treated.

### 7.2.1. Statistical analysis of the primary efficacy end point

The primary efficacy evaluation for measuring a clinical meaningful improvement is defined as demonstrating an improvement of the primary efficacy endpoint of 6-month objective response rate from 20% (under the null hypothesis) to 50% (under the alternative hypothesis) in the fully matched arm. With 5% one-sided type I error, we need to treat 20 patients to demonstrate the usefulness of the tri-therapy approach to achieve and 86% power based on the exact binomial test. With an expected 10% of patients who will be fully matched, we need to enroll 200 patients in the study. All inevaluable patients will be replaced. **To ensure that patients will not receive ineffective treatments after sufficient evidence, two efficacy futility early stopping rules** will be implemented.

- The first futility early stopping rule will be applied after treating 14 patients with the tri-therapy at the RP2D level. If none of the 14 patients has 6-month response (CR or PR), the patient enrollment will be halted and the trial can be stopped for futility. This futility early stopping rule coincides with the first stage of the Gehan's design targeting 20% response rate with 95% confidence (26).
- The second futility early stopping rule will be evaluated every 10 patients after 20 patients are treated at the RP2D by applying the predictive probability (27). The trial can be stopped early if we see the following 6-month responses or less: 2 in 20, 3 in 30, 5 in 40, 6 in 50, 7 in 60, 9 in 70, 11 in 80, or 12 in 90 patients. The design has 5% type I error rate and 95% power with a null response rate of 10% and a target response rate of 30% at 6 months in the whole group. The probability of early stopping is 0.95, 0.31, and 0.04 if the response rate in the whole group is 10%, 20%, and 30%, respectively.
- In addition to the futility analysis for early stopping of the trial if the triple therapy does not show minimum efficacy in the whole group, we will also look for efficacy signal in the subgroups. The triple therapy will be considered potentially effective if the posterior probability of response rate greater than 0.3 is larger than 60% in any of the predefined subgroups (Arm A, Arms B1-B3, Arms C1-C3, or any of the combined groups). Assuming a weak prior of Beta (0.1, 0.9), the treatment will be considered potentially efficacious if we see 4 responses in 10 patients, 7 responses in 20 patients, or 10 responses in 30 patients.
- In rare occasions that the early futility stopping criterion is met but the treatment shows potential efficacy in predefined subgroups, further discussions will be conducted among study PIs, sponsors, and regulatory agencies to determine whether study will be terminated or extended in specific subgroups.

These cohort size estimates are based on *in silico* data generated by SIMS using an independent set of data obtained from investigation of tumor and matched normal biopsies from the same patient. SIMS model will be considered clinically meaningful if the observed matches are similar to estimated matches, with a maximal tolerated coefficient of variability of 20%, and if fully matched group shows better outcome than partially matched groups.

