## 1.2. STUDY OVERVIEW

### **1.2.1. The first goal of the SPRING protocol is to test the safety and the activity of the selected tri-therapy in patients with metastatic NSCLC patients in first therapeutic line for the phase 2 portion of the trial (for the phase 1 patients with a maximum of 2 prior lines will be accepted).**

The trial will start with a Phase 1 safety study to establish the dose of each of the three agents. This part of the study will require about 30 patients treated (~40 patients enrolled). The Phase 1 will be followed by a first extension Phase 2 to test efficacy on up to 100 patients who will all receive the tri-therapy (100 patients treated/ ~120 patients enrolled (~20 patients screen failures)). All patients will have the necessary biopsies performed to ensure that adequate biopsy material is available before starting treatment. For ethical reasons, patients whose biopsies fail to produce interpretable data will still be treated with the tri-therapy. Pending clinical activity, the study may be extended by an additional 100 patients treated (total = 200 patients on the phase 2 portion) in order to firm up the initial efficacy assessment and identify the potential subgroups of patients with clinically meaningful efficacy.

Patients with specific documented oncogenic aberrations (EGFR mutations, ALK translocations, ROS1 if available and MET exon 14 skipping mutation if available) will be excluded from the trial. The study cohort will aim to include patients who are not generally treated with specific targeted therapeutics. Patients will be included in the study regardless of their PD1 or PD-L1 expression status. In the case of patients already treated on SPRING protocol who are later determined to have EGFR mutation or ALK translocation or ROS1 or MET exon 14 skipping mutations after SIMS analyses, amenable to treatment with an approved therapy, they will be given the option to continue investigational treatment in the SPRING trial after obtaining appropriate re-consent or discontinue treatment.

Early futility stopping rules will be applied in the phase 2 study should the tri-therapy have less than the expected efficacy to guard against patients being enrolled in ineffective treatment.

We estimate that overall 85% of the patients treated in the trial will have a profile that is matched to at least one out of the three drugs: 10% matched with three drugs, 36% matched with two drugs and 39% matched with one drug.

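### The stated 86% and 94% power hold only at exactly 20 fully matched patients; averaged over the number that 200 treated patients yield, power is about 84% and 91%, before any loss to unscored biopsies

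*Combined protocol and SAP*

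**What the plan says.** Section 7.2.1 sets the primary efficacy test as an improvement "from 20% (under the null hypothesis) to 50% (under the alternative hypothesis) in the fully matched arm". It continues "With 5% one-sided type I error, we need to treat 20 patients", giving "86% power based on the exact binomial test", and then "With an expected 10% of patients who will be fully matched, we need to enroll 200 patients in the study". Section 1.4 repeats these figures.

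Section 3.1 (Criteria of success) gives a second version: "With a type I error of 10% and a power of 94%, 20 patients fully matched will be enough", "assuming a null response rate of 20% based on the one-sided Fisher's exact test". It also arrives at 200, counted there as patients treated. Section 7.2 likewise speaks of 200 treated, and I read the total that way.

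On who can enter the fully matched arm (Arm A):

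- Section 7: SIMS is not used to assign patients. The score is expected within three months of starting treatment.
- Section 1.2.1: "patients whose biopsies fail to produce interpretable data will still be treated with the tri-therapy". Section 3.3.2 says the same for phase 2.
- Section 5.2.1: a SIMS score needs a minimum tumour content and a minimum normal epithelial content.
- Section 7: "The population for analysis of response (evaluable patients) will be those that received at least one cycle of treatment". Section 5.8 adds scan requirements. Neither asks for a SIMS score.
- Section 7.2.1: inevaluable patients are replaced.

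**The concern.** Both power figures are conditional on exactly 20 fully matched patients, but the plan fixes a different number, 200 treated. Twenty is only the expected yield at 10% prevalence. Because SIMS plays no part in selection, the actual count varies by chance, and no rule continues accrual until 20 fully matched patients have been scored.

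The plan also makes no room for treated patients without a score. The eight arms listed in Section 7 add up to the full 100 (10 + 13 + 12 + 15 + 11 + 8 + 16 + 15), so every treated patient is assumed to be scored. Yet the plan foresees failed biopsies and treats those patients. After one cycle they count as evaluable for response, but without a score they cannot be placed in Arm A. The roughly 120 enrolled per 100 treated covers screen failures before treatment (Section 1.2.1), so it does not absorb this loss.

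At stake is whether the extension to 200, which Section 3.1 justifies as attaining sufficient power, delivers the power quoted for it.

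**Working it through.** **Inputs.** Null rate 0.20 and alternative 0.50 (Sections 3.1 and 7.2.1); one-sided alpha 0.05 (7.2.1) or 0.10 (3.1); 10% fully matched and 200 treated (3.1, 7.2 and 7.2.1). The unscored fraction is not given, so it is an assumption, taken from 0% to 30%. Section 2.7 reports that 246 of 303 registered patients in the earlier study had dual biopsies. That is not a scoring-failure rate, and I do not use it as one.

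**Step 1: reproduce the stated figures at n = 20.** Reject when responses reach r, with r the smallest value such that P(X ≥ r | n, 0.20) ≤ alpha. Power is P(X ≥ r | n, 0.50).

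- Alpha 5%: r = 8, exact alpha 0.032, power 0.868 (stated 86%).
- Alpha 10%: r = 7, exact alpha 0.087, power 0.942 (stated 94%).

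Both reproduce with the one-sample exact binomial test. Section 3.1 names Fisher's test for the second. A two-sample one-sided Fisher test at 10% of 20 matched against 180 others, with true rates of 50% and 20%, has power of about 89%. The 94% is therefore the binomial figure under a Fisher label.

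**Step 2: distribution of the matched count.** With all 200 scored, K ~ Binomial(200, 0.10). The mean is 20, the SD is √(200 × 0.10 × 0.90) = 4.2, and the 5th to 95th percentiles are 13 to 27. P(K < 20) = 46.5%, so P(K ≥ 20) = 53.5%.

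**Step 3: average the power over K.** Average power = Σ P(K = k) × power(k), with r found afresh for each k. With all patients scored this gives 83.9% at 5% and 90.6% at 10%.

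**Step 4: scenarios for unscored patients.** If a fraction s of treated patients is scored, and scoring is unrelated to match status, K ~ Binomial(200, 0.10 × s).

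| Unscored (assumed) | Expected Arm A of 200 treated | P(at least 20) | Average power, 5% | Average power, 10% |
|---|---|---|---|---|
| 0% | 20 | 53% | 83.9% | 90.6% |
| 10% | 18 | 34% | 79.8% | 88.0% |
| 20% | 16 | 18% | 75.0% | 84.9% |
| 30% | 14 | 7% | 69.0% | 80.9% |

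Only the first row rests entirely on the plan's own inputs.

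**Note on single values of n.** Exact power is saw-toothed. At 5% it is 83.4% for n = 17, 76.0% for n = 18, 90.5% for n = 21 and 85.7% for n = 22. Comparing two single counts can mislead, so the average is the right summary.

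**The case against.** The strongest reply is that nothing is miscalculated. Both figures are presented as the power with 20 fully matched patients, both are right on that condition, and the word expected shows that 200 is an average yield. Quoting power at the expected subgroup size is common in planning. This stands: it is a planning and wording gap, not a wrong calculation. The gap remains because the plan attaches the power to a study of 200.

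The loss supported by the documents is small, and it is an average. A trial that scores more than 20 matched patients will often have at least the stated power. This also stands.

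A reader might infer from the table that true power is nearer 70% or 75%. The documents do not support that, because they give no failure rate. Section 1.2.1 has the biopsies done before treatment, and Section 5.2.1 asks for three to five samples, both of which limit failures.

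A reader might also infer that the plan expressly refuses to replace unscored patients. It does not. It replaces inevaluable patients and defines evaluable without reference to SIMS. The accurate statement is that nothing in the text replaces them.

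Nor is the count random because scoring comes late. Scores are due within three months, so the count can be seen as the trial runs. It is random because matching is not used for selection.

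Finally, the second 100 needs an amendment, Section 1.4 offers a SIMS-selected second cohort that could control the count, and Section 7.5 allows sample size re-estimation. These give chances to revisit the size. But the selected cohort is only one option, and the re-estimation is optional and tied to observed improvement rates, not to the match rate. Neither corrects the power now stated.

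**Conclusion.** The point holds in this form. On the plan's own inputs, 200 treated patients give average power of about 84% at one-sided 5%, against 86% stated (86.8% exact), and about 91% at 10%, against 94% stated. The chance of reaching 20 fully matched patients is 53%. That is a loss of about 2 to 3 points from chance variation in the matched count alone.

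Unscored biopsies can only add to the loss. Its size is unknown from the documents, and the 69% to 80% range at the 5% level is a set of scenarios, not an estimate.

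The results assume 10% prevalence, independent patients and the one-sample exact binomial test. They leave out futility stopping, which would lower power slightly further. They are also not the power of the whole success criterion in Section 3.1, which additionally asks that a 50% rate be achieved and that the fully matched arm be superior to the partially matched arms.

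**What to change.** In Sections 1.4, 3.1 and 7.2.1:

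1. Restate the power of the one-sample test as an average over the number fully matched: about 84% at 5% and 91% at 10% if all 200 treated patients are scored. The figures at exactly 20 can stay beside these, labelled as conditional.
2. Add a short scenario table by unscored fraction, as in the working, showing the expected Arm A count out of 200 treated.
3. State that the 94% comes from the one-sample exact binomial test, not from Fisher's test.

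The 200 should remain a count of treated patients. Redefining it as SIMS-scored patients would mean treating about 200/0.9 = 222, 200/0.8 = 250 or 200/0.7 = 286 patients at 10%, 20% or 30% unscored, which is a different and larger study.

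The cost is a few sentences and one table. No procedure changes and no patients are added. The only downside is a slightly less favourable stated power.
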